two cervical epidural steroid injections would be very appropriate in the treatment of a specific episode of cervical radicular pain. This literature also suggests that a maximum of four injections can be used within six months, assuming there was a positive response and improvement seen with the previous injections.

Study Design

This is a randomized, double-blinded clinical trial. The total enrollment goal is 60 patients (30 per treatment group)

Objective

The purpose of this study is to determine the effectiveness of cervical transforaminal epidural steroid injections in decreasing the need for an operation in patients with cervical radicular pain, otherwise considered to be operative candidates.

Treatment Groups:

Patients will be randomized in a 1:1 fashion to one of the following treatment arms:

1. Cervical transforaminal injection: 1.0 cc Lidocaine 1.0% with 1.0 cc normal saline
2. Cervical transforaminal injection: 1.0 cc Lidocaine 1.0% with 1.0 cc of Dexamethasone (10 mg/cc)

Primary/Secondary Outcome Variables

Primary Outcome Variables: The primary outcome variable is the avoidance of surgery. Treatment success is defined as the avoidance of surgery, while treatment failure is defined as having surgery due to failure of the injection treatment to alleviate pain and improve function over the 12 months they are being followed for purposes of this study.

Secondary Outcome Variables: Secondary outcome variables include:

- Decreased disability as measured by the validated outcome measure tool, the Neck Disability Index (NDI).
- Decreased neck pain and radicular pain as measured by a numerical pain rating, Verbal Numeric Pain Score with 0 being no pain and 10 being the worst pain imaginable
- Patient Satisfaction as measured by a numerical pain rating, Verbal Numeric Pain Score with 0 being completely unsatisfied and 100 completely satisfied

Patient Selection and Treatment Plan

Patients deemed to be surgical candidates for the treatment of cervical radicular pain at OrthoCarolina, PA will be screened for eligibility and asked to participate in the study. Potential subjects will meet with a research coordinator to discuss the details of the study. Those who choose to participate will be consented accordingly.

Inclusion Criteria:

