Study patients can elect to abandon the injection treatment and elect to undergo surgical treatment at any point during the course of the study. It is defined as treatment failure if a study patient elects to undergo surgical treatment. Patients who elect to undergo surgery will be discontinued from the study and no further effectiveness evaluations will be performed. Patients, referring physicians, and evaluating physician assistants are blinded to the treatment group. The treating physiatrist will not be blinded to the medications but will not be performing any clinical follow-up exams.

Follow-up Office Visits

Patients will be asked to return to the clinic 4 weeks, 12 weeks, 6 months, 12 months (following their first injection date) and the following data points will be collected for both groups:

- NDI questionnaire (disease specific measure), Verbal Numeric Pain Score, Blinding Assessment (patient and investigator), Pain Medication Use, Neurological Exam, and Subject satisfaction.

In the event that the patient receives their second, third, or fourth injection within 1 week prior to one of their follow-up office visits, the post injection phone call data will be collected at that visit. The study coordinator will tell the subject their baseline, pre-procedure Verbal Numeric Pain Rating and ask the subject to rate their current radicular pain intensity. Patients will also be asked to rate their overall satisfaction with their treatment and their current narcotic medication use.

The full schedule of assessments is shown in study flow chart below.

Study Flow Chart:

Study procedure	Screening	0 (day of procedure, injection #1)	Phone Call	Injection #2 (At least 14-21 days after #1)	4 weeks post injection	12 weeks post injection	6 months post injection	12 months post injection
Informed Consent	x							
Inclusion/Exclusion	x							
Verbal Numeric Pain Score**	x		x		x	x	x	x
NDI	x				x	x	x	x
Neuro Exam	x				x	x	x	x
Injection*		x		x				
Blinding Assessment - Patient					x	x	x	x
Blinding Assessment - Investigator					x	x	x	x
Pain Medication Use	x	x	x	x	x	x	x	x
Subject satisfaction			x		x	x	x	x
Adverse Events			x	x	x	x	x	x

* Patients may receive up to four injections within the 12 month period. Injections will be scheduled at least 14 days apart.

** Patients will be called one week after injection 1, 3 (as needed), and 4 (as needed)

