***If an injection occurs within 1 week prior to follow-up visits, patient will not be called. Verbal Numeric Pain Scale, Pain Medication Use, Subject Satisfaction and Adverse Events will be recorded during the follow-up visit.

Unblinding Procedures

Patients will not be unblinded to their study treatment. Unblinding of patients will only occur by the data manager and statisticians in the event of an SAE that is deemed possibly or probably related. Subjects that have been “blind-broken” must be discontinued from the study and no further effectiveness evaluations will be performed. However, the SAE will continue to be followed up until resolution.

Sample Size

Sample size calculations are based on the study by Riew et al. (2000). We estimate that 30% patients randomized to Lidocaine will avoid surgery compared to 70% of the patients randomized to Lidocaine with Dexamethasone. With a level of significance of 0.05 and power of 80%, 23 patients are needed in each group. To account for a 30% attrition rate, 30 patients are needed in each group. The total enrollment goal is 60 patients.

Risks

As with all medications, side effects may include an allergic reaction. Allergic reactions may range from minor reactions, such as itching or rash, to major, life-threatening reactions which can result in death.

Risks associated with cervical transforaminal injections include, but are not limited to:

Likely

- Spinal headache;

Less Likely

- Nerve irritation;
- Nerve injury;
- The risk of bleeding and/or infection into the spinal area;
- Reaction to medications;

Rare, but Serious

- Lung collapse;
- Seizures
- Paralysis
- Loss of vision
- Stroke
- Death.

Risks of general anesthesia or moderate sedation include, but are not limited to:

The most common side effects may include:

- Headache
- Adverse reaction to medications

Less common side effects of may include:

- Bleeding sufficient to cause anemia or require transfusion
- Hematoma (bleeding from the procedure)
- Pseudoaneurysm (injury to a blood vessel)
- Seroma (a collection of fluid under the skin)
- Blood vessel injury
- Pneumonia

Rarely, side effects may include:

- Hypotension (drop in blood pressure)
- Cardiopulmonary arrest (heart attack)
- Stroke
- Pulmonary embolism (a blood clot to your lungs)

- Death

Risks associated with contrast agents that are used in the procedure include, but are not limited to:

- Allergic reaction
- Anaphylaxis
- Death

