- **Informed Consent**
Informed consent will be obtained for each patient. One copy of the informed consent will be given to each patient, a copy will be placed in the medical records, and the original signed copy will be retained in the investigator's study records. The protocol and the patient informed consent will have the approval of a properly constituted IRB responsible for approving clinical studies. Any changes to the protocol will be approved by the IRB and any changes to the informed consent must be approved by the IRB.
- **Applicable regulations**
This is an Investigator Initiated Research Study and will be conducted in compliance with the protocol approved by the Institutional Review Board, and according to Good Clinical Practice standards. No deviation from the protocol will be implemented without the prior review and approval of the IRB except where it may be necessary to eliminate an immediate hazard to a research subject. In such case, the deviation will be reported to the IRB as soon as possible.

Records Retention

All patient records including written informed consent forms, the protocol, and IRB correspondence will be kept for a minimum of three years from the date of termination of this study.

Data Collection forms

See Attached forms

Definition of Subject Completion, Withdrawal, and Premature Discontinuation

Subject completion

A subject will be considered to be completed if the patient completes all study procedures and follow-up.

Withdrawal and Premature Discontinuation

Patients may be withdrawn or prematurely discontinued from the study of their own volition or at the discretion of the investigator. Any patient may decide to withdraw from the study at any time without being penalized. The investigator and/or anesthesiologist will discontinue the patient from the study, if, for any reason, he/she feels that the continued participation would not be in the best interest of the patient.

Study Completion and Termination

The study is completed when the desired sample size of patients have completed the study or if the investigator feels that the study should no longer continue. The institutional review board will be notified of study completion and/or termination.

References

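### Patients whose blind is broken leave the study with only the SAE followed, so their 12-month surgery status, the primary outcome, may go unrecorded

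*Combined protocol and SAP*

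**What the plan says.** **Unblinding Procedures.** The data manager and statisticians may break the blind "in the event of an SAE that is deemed possibly or probably related". Once that happens the subject "must be discontinued from the study and no further effectiveness evaluations will be performed". One activity is kept: "However, the SAE will continue to be followed up until resolution". The patient stays blind: "Patients will not be unblinded to their study treatment".

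**Primary/Secondary Outcome Variables.** Success is avoidance of surgery and failure is surgery because the injections did not work, assessed "over the 12 months they are being followed for purposes of this study".

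**Third and Fourth Injections (as needed).** Patients who choose surgery leave the study under nearly the same wording: "Patients who elect to undergo surgery will be discontinued from the study and no further effectiveness evaluations will be performed". Their outcome, however, is assigned: "It is defined as treatment failure if a study patient elects to undergo surgical treatment".

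**Definition of Subject Completion, Withdrawal, and Premature Discontinuation.** "A subject will be considered to be completed if the patient completes all study procedures and follow-up". The section describes withdrawal but no data collection after it.

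**Data Safety Monitoring Plan.** SAEs judged related, probably related or of unknown relatedness to the study procedure are e-mailed to the DSMB as they occur.

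**The concern.** A patient who chooses surgery and a patient whose blind is broken are discontinued in almost the same terms, but only the first has a known primary outcome. A patient unblinded before any surgery has no assigned outcome, and no visit is left at which one would be recorded.

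The loss would follow an event after randomisation that was judged possibly or probably related, so it cannot be treated as random. It could bias the surgery comparison. A difference between arms is possible but not shown: the serious procedural risks listed in the Risks section apply to both arms. The plan also does not say whether such a patient is dropped, counted as having avoided surgery or counted as a failure.

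The smaller issue is that the relatedness categories that permit unblinding are not those that trigger the DSMB e-mail.

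**Working it through.** **1. Is surgery status collected anywhere else after unblinding?**

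| Section | What it offers |
|---|---|
| Unblinding Procedures | SAE follow-up only |
| Follow-up Office Visits and Study Flow Chart | No surgery-status item for any patient |
| Completion and withdrawal definitions | No follow-up after discontinuation |
| Statistical analysis | Incidence of surgery avoidance; no analysis set and no missing-data rule |

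No section collects or assigns the outcome for these patients. The term effectiveness evaluations is not defined, and later surgery might still become known at the site. The text therefore supports *may be lost*, not *will be lost*.

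**2. Effect at the planned rates.** The Sample Size section gives 30% v 70% avoiding surgery and 30 patients per group, that is 9/30 v 21/30. (Its 23 evaluable per group is close to the 23.3, rounded up to 24, from the two-sided pooled formula without continuity correction. The present point does not depend on it.) The uncorrected chi-square is N(ad − bc)² / (product of the four margins):

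60 × (9×9 − 21×21)² / 30⁴ = 60 × 360² / 810,000 = 9.60, p = 0.0019.

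Removing one patient:

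| Patient lost | Control v steroid | Difference (points) | p |
|---|---|---|---|
| None | 9/30 v 21/30 | 40.0 | 0.0019 |
| Steroid success | 9/30 v 20/29 | 39.0 | 0.0028 |
| Steroid failure | 9/30 v 21/29 | 42.4 | 0.0011 |
| Control success | 8/29 v 21/30 | 42.4 | 0.0011 |
| Control failure | 9/29 v 21/30 | 39.0 | 0.0028 |

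One unknown patient in 30 leaves 1/30 = 3.3 points of that arm's rate open.

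**3. Effect on a borderline result** (an illustration, not a forecast):

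| Control v steroid | Uncorrected | Continuity-corrected | Fisher exact |
|---|---|---|---|
| 11/30 v 19/30 | 0.039 | 0.071 | 0.070 |
| Steroid success lost, 11/30 v 18/29 | 0.051 | 0.091 | 0.070 |
| Steroid failure lost, 11/30 v 19/29 | 0.027 | 0.051 | 0.038 |

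The uncorrected test crosses 0.05 when a success is lost, Fisher's test crosses it when a failure is lost, and the corrected test does not cross. The plan names the chi-square test without saying whether a correction is used.

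**4. Power.** The number of unblindings is not given. Assuming 0 to 3, all in the steroid arm, two-sided power at 30% v 70% falls from 89.3% to 87.5% starting from 30 per arm, and from 79.4% to 76.3% starting from 23 per arm. Precision is not the main issue.

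**5. Length of the gap.** If the blind were broken at the 4-week, 12-week or 6-month visit, 52 − 4 = 48, 52 − 12 = 40 or 52 − 26 = 26 weeks of surgery status could go unobserved. SAEs need not fall at visits, so these figures only indicate scale.

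**6. Relatedness categories.** Unblinding: possibly, probably. DSMB e-mail: related, probably related, unknown. Only probably related is on both lists. A possibly related SAE can therefore break the blind without triggering the automatic e-mail. The unblinding rule also does not say what the SAE must be related to.

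**The case against.** The strongest reply is that loss of the outcome is inferred. The undefined term may mean only the scheduled instruments (disability index, pain score, neurological examination, satisfaction). Surgery is an event that the site would usually learn of, because the patients are surgical candidates at the same practice. The flow chart has no surgery row for anyone, so its silence says nothing special about this group. The data collection forms are attached to the protocol but not available here, and they may capture surgery after discontinuation. All of this is fair and limits the claim to possible loss. It does not supply a planned way of collecting the outcome, and the instruction to discontinue is mandatory.

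A second reply is that the gap is general. The plan allows for 30% attrition, which is 9 of 30 per arm, and related SAEs would probably be a small part of that. This stands: a general rule on surgery status after any discontinuation would cover this case too. The unblinding rule still needs its own wording change, because it stops follow-up explicitly.

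A third reply is that the numbers are small and the borderline example depends on the test chosen. That is also true, and it limits the weight of the point.

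On relatedness, SAEs still reach the IRB within 24 hours and the DSMB reviews them every other month or as needed. Only the automatic e-mail is at stake.

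**Conclusion.** The concern holds, with medium confidence. As written, the plan stops effectiveness follow-up for unblinded patients and neither collects nor assigns their 12-month surgery status. The effect is probably small: 3.3 points of an arm's rate per patient, and no change of conclusion at the planned rates if one patient is lost. It could decide a close result. This rests on few unblindings (no rate is given) and on the unseen forms not already recording surgery after discontinuation. The documents show no need for the loss: the patient remains blind to treatment and the outcome is a simple yes or no. The relatedness mismatch is real but minor. Overall this is an inexpensive improvement that should be made.

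**What to change.** - **Unblinding Procedures:** amend the wording, including the requirement to discontinue from the study, so that discontinuation does not end the recording of surgery status (yes/no and date) to 12 months, subject to the patient's consent. What happens to study treatment and the other assessments stays with the sponsor.
- **Statistical analysis:** state that these patients are analysed in the arm to which they were randomised.
- **Completion and withdrawal definitions:** preferably add a general rule that surgery status is recorded to 12 months after any discontinuation, on the same consent condition.
- **Unblinding Procedures and Data Safety Monitoring Plan (minor):** reconcile them to one relatedness scale that says what the event is related to, so that any category permitting unblinding also triggers the DSMB e-mail.

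The cost is wording in a few sections, a record check or one call for a few patients, and possibly a few more DSMB e-mails. If the forms already record surgery after discontinuation, or use a single relatedness scale, the corresponding change is only a correction of wording.

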Normality testing will be conducted for all continuous variables. Standard descriptive statistics will be calculated for patient demographic variables as well as the primary and secondary outcome variables. For variables measure at the ordinal level (i.e. categorical data) frequencies and percentages will be reported. Mean and standard deviation will be reported for all normally distributed data measured as intervals or ratios (i.e. continuous data). Median and interquartile range will be reported for continuous variables that are skewed. The incidence of surgery avoidance will be calculated. Bivariate analyses will be conducted to determine the associations between surgery avoidance and age, gender, pain, function, pain medicine consumption, BMI and subject satisfaction. Chi-Square tests will be used for categorical data and t-test or the nonparametric equivalent will be used for continuous data.

Adverse Event Reporting

Adverse events such as, death or any other complication will be reported to the IRB.

Subjects will be instructed to report any "Serious Adverse Event" immediately to the investigator.

"Serious Adverse Event" is defined as any event that:

- Results in death
- Is life-threatening
- Results in persistent or significant disabling/incapacity
- Requires inpatient hospitalization or prolongation of hospitalization
- Is a congenital abnormality/birth defect
- Requires medical or surgical intervention to prevent permanent impairment or damage

Serious adverse events will be reported to Presbyterian Healthcare Institutional Review Board within 24 hours of the event. This report may be done by phone initially and will follow with an adverse event report form.

Data Safety Monitoring

A Data Safety Monitoring Board will review data for integrity.

[name]., Chairman, Research Committee will serve as the safety monitor. A data safety monitoring board (DSMB) will review data on a bi-monthly basis or as needed. The DSMB are members of the OrthoCarolina Research Institute (OCRI) Research Advisory Committee.

Data Safety Monitoring Plan

Serious adverse events (SAEs) that are "related," "probably related" or have an "unknown" relatedness to the study procedure, will be reported to the data safety monitoring board via email as they occur. The data safety monitoring board meets every

other month. At each meeting the study will be reviewed for adverse events, serious adverse events, and overall feasibility issues.

Ethical and Regulatory Considerations

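### The allowance for 30% attrition is miscalculated: 30 per group leaves 21 evaluable, not the required 23, and power falls to about 75% if lost patients are excluded

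*Combined protocol and SAP*

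**What the plan says.** The Sample Size section assumes that 30% of patients on lidocaine alone and 70% on lidocaine with dexamethasone will avoid surgery. It then states: "With a level of significance of 0.05 and power of 80%, 23 patients are needed in each group". The next sentence is: "To account for a 30% attrition rate, 30 patients are needed in each group". The resulting target of 60 patients, 30 per arm, is repeated under Study Design.

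The section does not state whether the test is one-sided or two-sided, which sample-size formula was used, how the inflation was done, or what counts as attrition. On testing, the Statistical analysis section says: "Chi-Square tests will be used for categorical data". The plan gives no rule for how patients lost before 12 months enter the primary analysis.

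Two sentences at the end of the section on third and fourth injections bear on the meaning of attrition. One reads: "It is defined as treatment failure if a study patient elects to undergo surgical treatment". The other reads: "Patients who elect to undergo surgery will be discontinued from the study and no further effectiveness evaluations will be performed".

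**The concern.** An attrition allowance should make the number left after losses equal the number the power calculation needs. Here it does not: by the plan's own figures, 30% attrition leaves fewer than 23 per group. The likely cause is multiplying by 1.3 where division by 0.7 is needed.

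This is the only power justification in the document. If losses reach the level the sponsor planned for, a null result would be read as coming from a trial with 80% power when the actual figure was lower.

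The undefined term adds to the difficulty. Patients who have surgery leave the study, but their primary outcome is known. If they were counted as attrition, the 30% allowance would be exceeded by design.

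**Working it through.** **Inputs (Sample Size section unless noted).** Surgery avoidance p₁ = 0.30 and p₂ = 0.70, so the difference is 0.40 and the mean is 0.50; alpha 0.05; power 80%; 23 per group before attrition; attrition 30%; 30 per group enrolled. Allocation is 1:1 (Randomization section). *Assumptions:* two-sided test, no continuity correction, lost patients excluded from the primary analysis.

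**Step 1: reproduce the plan's 23.** Pooled normal formula:

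n = [1.96 × √(2 × 0.5 × 0.5) + 0.8416 × √(0.3 × 0.7 + 0.7 × 0.3)]² / 0.40² = (1.386 + 0.545)² / 0.16 = 23.3

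The arcsine formula gives 23.2. The plan's 23 is therefore reproduced, apart from rounding down.

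**Step 2: the inflation.**
- Multiplying: 23 × 1.3 = 29.9, so 30. This is the plan's figure.
- Dividing: 23 / (1 − 0.30) = 32.9, so 33. Check: 33 × 0.7 = 23.1.
- What 30 leaves at 30% loss: 30 × 0.7 = 21, two short of 23.
- What loss 30 can absorb: 1 − 23/30 = 23.3%, or 7 patients per group.

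**Step 3: power at each evaluable number.** The pooled normal power is Φ{[0.40 × √n − 1.96 × √0.5] / √0.42}. At n = 21 this is Φ[(1.833 − 1.386) / 0.648] = Φ(0.690) = 75.5%. The exact column enumerates all outcomes of the uncorrected chi-square.

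| Evaluable per group | Loss from 30 | Pooled normal | Exact chi-square |
|---|---|---|---|
| 21 | 30% | 75.5% | 74.8% |
| 22 | 26.7% | 77.5% | 77.8% |
| 23 | 23.3% | 79.4% | 80.9% |
| 30 | 0% | 89.3% | 89.6% |

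The drop from 23 to 21 is 79.4 − 75.5 = 3.9 points, or 80.9 − 74.8 = 6.1 points. The difference detectable with 80% power at 21 per group, with rates symmetric about 50%, is about 42 percentage points (0.420 normal, 0.424 exact) against about 40 at 23 (0.403 and 0.396).

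**Step 4: does the unstated sidedness matter?** A one-sided test with continuity correction also gives 23 (22.97). Its power is 80.1% at 23 and 75.7% at 21, so the result is similar.

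**Step 5: surgery is not attrition.** At the plan's own rates, expected surgeries are 30 × 0.70 + 30 × 0.30 = 21 + 9 = 30 of 60 patients. Counting them as lost would put attrition at 50%. The 30% can only sensibly mean loss of surgery status.

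**The case against.** Four points can be made in the plan's favour.

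- **Lost patients might not be excluded.** The plan has no rule for missing outcomes. If all 30 per group were analysed at unchanged rates, power would be about 89%. That is true, but no inflation would then be needed; the inflation step itself implies that lost patients leave the count. The conclusion remains conditional on exclusion.
- **The figure of 75% depends on the test.** This stands. The chi-square sentence follows a list of bivariate analyses that does not include treatment group, and no continuity correction is mentioned either way. With a Yates-corrected chi-square or Fisher's exact test, exact power is 71.3% at 23, 62.9% at 21 and 83.8% at 30. The choice of test therefore moves power more than the inflation error does. It does not rescue the sentence, since the shortfall from 23 to 21 is the same under any test.
- **Another formula gives 80% at 21.** The unpooled formula gives 80.7% at 21 per group. But it also gives a requirement of 20.6, or 21, so it is not how the plan reached 23.
- **The shortfall is small.** It is two evaluable patients per group, and arises only if losses exceed 23.3%. This stands, and it limits the weight of the point.

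**Conclusion.** The concern holds. Thirty per group does not retain the plan's own 23 at 30% attrition; it retains 21. That part is arithmetic on three numbers in adjacent sentences and needs no assumption about the test. With lost patients excluded, 60 enrolled cannot deliver both the stated attrition allowance and the stated power.

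The size is modest: 3 patients per group (6 in total) below the matching enrolment, or about 4 to 6 points of power, giving about 75%. The power figure rests on a two-sided 0.05 level, an uncorrected chi-square and the plan's rates of 30% and 70%. The one-sided variant that also reproduces 23 gives nearly the same answer. If losses stay at or below about 23%, the requirement of 23 is met. The error introduces no bias in the treatment comparison.

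**What to change.** Keep 60 patients and replace the attrition sentence in Sample Size with wording such as:

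> With 30 patients per group, 23 per group remain evaluable if surgery status is lost for no more than 7 per group (about 23%). If 30% are lost and excluded, 21 per group remain and power is about 75% (two-sided 0.05, uncorrected chi-square, 30% against 70%). Patients who have surgery are treatment failures with a known primary outcome and are not counted as attrition.

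Two details need settling with it. The test and sidedness in the brackets are assumptions and should match the primary analysis the sponsor intends; if that is a continuity-corrected or Fisher test, the figure at 21 is 62.9%. The last sentence also has to agree with the outcome definition. Primary/Secondary Outcome Variables ties failure to surgery done because the injections did not work, whereas the section on third and fourth injections counts any elected surgery. Those two passages should be reconciled.

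The alternative is to keep the 30% allowance and enrol 33 per group (66 in total), or 35 per group (70 in total) if the 23.3 is rounded up to 24 first (24 / 0.7 = 34.3).

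Restating costs one sentence and a one-line definition. It adds no patients or procedures; the only price is a slightly less favourable stated power at 30% loss.

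### With 30% attrition planned and no denominator stated, the crude incidence of surgery avoidance does not recover the 12-month rate in either arm; a Kaplan-Meier estimate would under independent censoring

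*Combined protocol and SAP*

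**What the plan says.** The section Primary/Secondary Outcome Variables makes the endpoint binary: "Treatment success is defined as the avoidance of surgery, while treatment failure is defined as having surgery due to failure of the injection treatment", judged "over the 12 months they are being followed for purposes of this study". The text after Third and Fourth Injections (as needed) lets a patient choose surgery at any time, and adds: "It is defined as treatment failure if a study patient elects to undergo surgical treatment". Such a patient then leaves the study with the outcome already known.

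The Sample Size section expects substantial loss: "To account for a 30% attrition rate, 30 patients are needed in each group". The section on withdrawal and premature discontinuation lets patients leave when they wish, or be withdrawn by the investigator.

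For the analysis, the Statistical analysis section says: "The incidence of surgery avoidance will be calculated". It also names chi-square as the general test for categorical variables, which is the only sentence that could cover a comparison of arms on this endpoint. No section names Kaplan-Meier, log-rank or any other method for censored data. None states the denominator of the incidence, or how to count a patient lost before 12 months without surgery.

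**The concern.** The two outcomes become known at different times. A patient operated on in month 2 is a recorded failure whatever would have happened to follow-up later. A patient who leaves in month 10 without surgery has ten surgery-free months on record but no 12-month status. If such patients are left out, the set with known outcome is short of would-be successes even when dropout has nothing to do with prognosis. If they are counted one way or the other, the rate moves down or up by an amount set by the attrition and not by the treatment.

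The avoidance percentage in each arm is the trial's headline figure. Readers will set it beside the avoidance rates that the Background quotes from earlier series.

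**Working it through.** **1. The plan's own figure.** Inputs from Sample Size: avoidance of 30% on lidocaine and 70% with dexamethasone added, alpha 0.05, target power 80%, and a stated result of 23 per group. Allocation is 1:1. The test is assumed two-sided, as the plan does not say.

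n = [1.96 × √(2 × 0.5 × 0.5) + 0.8416 × √(0.3 × 0.7 + 0.7 × 0.3)]² / 0.4² = (1.386 + 0.545)² / 0.16 = 23.3.

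Rounded up this is 24. Exact chi-square power at 23 per group is 0.809, so 23 is reproduced. The figure of 30 matches 23 × 1.3 = 29.9. Adding patients for attrition makes sense only if lost patients are to drop out of the analysis. That is an inference; the plan does not write it.

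**2. Set-up for the check (assumptions, not in the documents).** Constant surgery hazards that give 30% and 70% avoidance at 12 months, and independent dropout at a constant hazard that would reach 30% by 12 months without surgery. With time in years:
- Surgery hazard: −ln 0.3 = 1.204 (lidocaine); −ln 0.7 = 0.357 (dexamethasone).
- Dropout hazard: −ln 0.7 = 0.357 in both arms.
- Observed success = avoidance × 0.7.
- Observed surgery = [surgery hazard / (surgery + dropout hazard)] × (1 − observed success).
- Lost = the remainder.

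Lidocaine: success 0.3 × 0.7 = 0.210; surgery (1.204/1.561) × 0.790 = 0.609; lost 0.181.
Dexamethasone: success 0.7 × 0.7 = 0.490; surgery 0.5 × 0.510 = 0.255; lost 0.255.

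**3. The crude rate under each way of counting lost patients, 30 per arm.**

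| Lost patients | Lidocaine (true 30%) | Dexamethasone (true 70%) | Difference | Chi-square power |
|---|---|---|---|---|
| Excluded | 0.210/0.819 = 25.6% | 0.490/0.745 = 65.8% | 40.1 points | 0.81 |
| Counted as failures | 21% | 49% | 28 points | 0.63 |
| Counted as successes | 21.0 + 18.1 = 39.1% | 49.0 + 25.5 = 74.5% | 35.4 points | 0.81 |

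None of the three returns 30% and 70%. Kaplan-Meier does under the same assumptions, in closed form and in simulation.

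**4. Other timing patterns, lost patients excluded.** Simulations crossed early, uniform, exponential or late dropout with falling, constant or rising surgery hazards (12 scenarios, 8,000 trials each). The crude rate ran from 23% to 29% in the 30% arm and from 62% to 70% in the 70% arm, a shortfall of about 0 to 8 points. It almost vanishes when dropout is early and surgery late. The difference stayed at 39 to 41 points and chi-square power at 0.77 to 0.83.

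**5. Heavier reading of the 30%.** If 30% of randomised patients are actually lost before surgery, exclusion gives 23.6% and 63.6%, with power 0.76.

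**6. What other methods would do.**
- Log-rank power was 0.78 to 0.90 over the 12 scenarios, about 1 to 7 points above chi-square on known outcomes.
- A comparison of 12-month Kaplan-Meier estimates under constant hazards had power 84% on the plain scale, but rejected about 6% of the time under the null. On the log-log scale it had power 81% with null rejection 4.7%.
- With the same true 30% and 70% but non-proportional hazards (Weibull shape 2 for lidocaine, 0.6 for dexamethasone), log-rank power fell to 60%, against about 75% for chi-square.
- With true 12-month avoidance equal at 30% and only the timing different, log-rank rejected in 29% of trials and chi-square in 5%.

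**The case against.** The strongest reply is that a binary endpoint at a fixed horizon is legitimate, that the comparison of arms is hardly disturbed, and that the documents do not fix the direction of any bias. Most of this stands, and it limits the point in four ways.

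- A reader might infer that the plan's rates are biased low without qualification. The documents do not support that. They give no denominator, and on the failure definition taken literally a patient who leaves without surgery is not a failure. Counted as a success, that patient pushes both rates up. Understatement follows only if lost patients are excluded or counted as failures.
- A reader might infer that the treatment effect is distorted or the trial underpowered for this reason. With exclusion, the difference stays near 40 points and power near 80%. A large loss of power (to 0.63) arises only if lost patients count as failures.
- A reader might infer that the log-rank test should become the primary analysis. The endpoint is avoidance at 12 months, not delay. The log-rank test responds to timing as well, so it could credit a treatment that only postpones surgery, and its power advantage reverses under some non-proportional patterns. Nor can a gain from a covariate-adjusted Cox model be claimed, since the documents give no prognostic hazard ratio.
- A reader might infer that surgery dates are not collected. The data collection forms are attached to the protocol but not shown, so this cannot be said.

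Kaplan-Meier also needs independent censoring, which withdrawal at the investigator's discretion could break. But the crude rate among known outcomes is biased even when censoring is independent, so this does not favour the crude rate.

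**Conclusion.** The point holds in limited form. The plan reduces a dated event to a crude incidence, plans for 30% attrition, and does not say how lost patients enter. Under constant hazards and independent dropout, none of the three crude denominators gives the true per-arm rates. On the implied reading (exclusion) the understatement is about 4 points in each arm, with a range of about 0 to 8 by timing. The alternatives err more under the same assumptions: 9 and 21 points too low, or 9.1 and 4.5 points too high.

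This is a weakness in the reported rates and in the definition of the analysis. It is not evidence that the comparison of arms is invalid. The sizes rest on assumed timing of surgery and dropout, independent dropout and a two-sided test, none of which the documents give. The recommended estimator is justified by less bias in the two rates; on the better-calibrated log-log scale it brings no gain in power.

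**What to change.** In the Statistical analysis section:

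1. Keep avoidance of surgery at 12 months as the primary endpoint. Estimate it in each arm by Kaplan-Meier, with time from first injection to surgery censored at last contact or 12 months.
2. Report the 12-month difference between arms with a 95% confidence interval suited to small samples (for example, built from log-log transformed estimates). Under the assumptions above only about 0.21 × 30 = 6 lidocaine and 0.49 × 30 = 15 dexamethasone patients would be under observation and surgery-free at 12 months, and the plain Wald version rejects about 6% under the null.
3. Report the crude proportion and chi-square test as well, with the denominator stated. Counting all lost patients as failures, and then as successes, gives simple bounds on each rate.
4. Use the log-rank test as supportive only, and say that it addresses timing as well as 12-month avoidance.
5. Make sure the dates of surgery and of last contact are captured, and state which date defines the event, since one section speaks of having surgery and another of electing it.

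The cost is a few sentences of analysis wording, a check that two dates are on the forms, and slightly more analysis work. No extra patients or visits are needed. The downside is reliance on independent censoring, so reasons for withdrawal should be reported by arm.
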